## **7.5. Preparation/Handling/Storage/Accountability**

A description of the methods and materials required for preparation will be detailed in the pharmacy manual.

- Only participants enrolled in the study may receive study treatment and only authorized site staff may prepare, handle, supply or administer study treatment. All study treatments must be stored in a secure environmentally controlled and monitored (manual or automated) area in accordance with the labelled storage conditions with access limited to the Investigator and authorized site staff.
- For the double-blind phase of the study, the Unblinded Pharmacist or designee is responsible for study treatment accountability, reconciliation, and record maintenance (i.e. receipt, reconciliation and final disposition records).
- Under normal conditions of handling and administration, study treatment is not expected to pose significant safety risks to site staff. In the case of unintentional occupational exposure notify the unblinded monitor, Medical Monitor and/or the Sponsor study contact.
- A Material Safety Data Sheet (MSDS)/equivalent document describing occupational hazards and recommended handling precautions either will be provided to the Investigator, where this is required by local laws, or is available upon request from the Sponsor.

## **7.6. Compliance with Study Treatment Administration**

For the double-blind phase of the study only, the individual dose for a participant is prepared by an unblinded Pharmacist, licensed Pharmacy Technician, or designee. The

preparation of the dose will be reviewed and confirmed by a second unblinded member of the study site staff.

For the double-blind phase of the study only, the IP will be administered by an unblinded designee. For the double-blind phase and the OLE, the date and time of each dose administered along with the location of each injection identified by syringe number, will be recorded in the source documents. The location/syringe number and study participant identification will be confirmed at the time of dosing by a member of the study site staff (blinded to study treatment) other than the person administering the study drug.

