# **7. STUDY TREATMENT**

## **7.1. Investigational Product and Other Study Treatment**

The term study treatment is used throughout the protocol to describe RVT-1401 or placebo.

To maintain the study blind within the double-blind phase of the study, all participants will receive two injections (2 ml volume each) by an unblinded designee (Section 7.6); participants receiving the 680 mg dose will receive two injections of RVT-1401, while participants receiving the 340 mg dose will receive one injection with RVT-1401 and one

placebo injection. Participants receiving placebo will receive two injections of placebo. The blinded syringes will be numbered so that any injection site reaction can be assigned to a specific syringe number and medication #.

The OLE is open-label. Each participant will receive 3 additional doses of RVT-1401, once every 2 weeks, as a single 340 mg injection over a 6-week period.

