## 7.4. Packaging and Labeling

RVT-1401 will be supplied to the study site as a sterile liquid formulation with a nominal fill of at least 1 mL in Nuova Ompi 2R clear glass vials with a flip-off cap. The solution is clear to slightly yellow, essentially free of visible particles, for SC administration. ■■■

Placebo will be provided as a sterile liquid formulation with at least a 1 mL fill in Nuova Ompi 2R clear glass vials with a flip-off cap. The solution is clear, essentially free of visible particles, for SC administration.

Doses will be prepared by the unblinded pharmacist or designee with a label that includes at a minimum the study number, participant number, medication number and vial number. Doses are administered to participants by pre-identified unblinded clinic staff or designee.

See Pharmacy Manual for exact instructions on dose preparation.

All labels will meet all local applicable requirements and Annex 13 of Good Manufacturing Practices: Manufacture of investigational medicinal products (July 2010) and/or other local regulations as applicable.

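### A blinded staff member checks the syringes at every double-blind dose although the two solutions may at times look different: a potential unblinding route that is cheap to close

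*Protocol*

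**What the plan says.** Protocol 7.4 describes the two products separately. For RVT-1401: "The solution is clear to slightly yellow, essentially free of visible particles, for SC administration". For placebo: "The solution is clear, essentially free of visible particles, for SC administration". It refers the detail elsewhere: "See Pharmacy Manual for exact instructions on dose preparation".

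Under Protocol 7.1 every participant receives two 2 mL injections per double-blind dose. The 680 mg arm has two active syringes and the placebo arm two placebo syringes, while "participants receiving the 340 mg dose will receive one injection with RVT-1401 and one" of placebo. On the syringes themselves it says: "The blinded syringes will be numbered so that any injection site reaction can be assigned to a specific syringe number and medication" number.

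Protocol 7.6 has unblinded staff prepare each double-blind dose and a second unblinded person confirm the preparation, and "the IP will be administered by an unblinded designee". It then requires that injection location, syringe number and participant identity "will be confirmed at the time of dosing by a member of the study site staff (blinded to study treatment", someone other than the person injecting.

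On rating, Protocol 8.5.1 to 8.5.3 let trained physicians, coordinators, clinic personnel or evaluators administer the MG-ADL, QMG and MGC. Protocol 11.6 gives adverse-event causality to the investigator. No section says whether dosing staff may also rate.

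**The concern.** Giving preparation and injection to unblinded staff is the usual arrangement when active and placebo might be told apart. The 7.6 check works against it by placing a blinded colleague next to the filled syringes at every dose. If a tint were visible, that person could form a view of the assignment and later rate the participant or speak to someone who does.

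The exposed outcomes are those that depend on judgement: MG-ADL (patient-reported), MGC (part physician, part patient), QMG to a lesser degree because it is built on quantitative testing, and adverse-event causality. SAP 9.2 places MG-ADL change and MG-ADL response in its conditional testing sequence, and SAP 8.3 gives clinical response co-primary importance. With about 21 participants in three arms, roughly seven per arm, a few influenced ratings could matter to a responder comparison.

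The sponsor already treats this as a risk area. SAP 4 lists clinical trial material among its four possible sources of unblinding, and Protocol 7.3 withholds IgG, albumin, total protein, alkaline phosphatase and anti-AChR results from sites.

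**Working it through.** There is no figure in the plan to reproduce. The check compares the text of several sections and adds a simple count.

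**1. What the colours could tell a viewer.** Inputs are the two descriptions in Protocol 7.4 and the syringe allocation in 7.1. Suppose the contents can be seen.

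- If the active solution is visibly tinted: 680 mg shows two tinted syringes, 340 mg shows one tinted and one untinted side by side, and placebo shows two untinted.
- If the active solution is not visibly tinted: all three arms show two untinted syringes.

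The information is therefore one-sided. A tinted syringe points to active drug. Two untinted syringes fit any arm, because the description of RVT-1401 includes a clear solution.

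**2. Who is near the syringes at a double-blind dose.**

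- Preparer (7.6): unblinded.
- Second person confirming preparation (7.6): unblinded.
- Injector (7.4, 7.6): unblinded.
- Person confirming syringe number, location and identity at dosing (7.6): blinded.

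Only the last role brings a blinded staff member to the syringes by rule. The task itself (number, location, identity) does not need a blinded person.

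**3. Timing against the MG scores.** The footnotes to the tables in Protocol 8.1 and 8.2 put MG assessments before dosing on dosing days. With two syringes per dose, the number checked before the score at dosing visit k is 2 x (k - 1).

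- Baseline, k = 1: 2 x 0 = 0
- Second dose, k = 2: 2 x 1 = 2
- Sixth dose, k = 6: 2 x 5 = 10
- Week 7, after all six doses: 6 x 2 = 12

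Baseline scores are clean. Twelve is an upper limit for any one checker, reached only if the same person attends all six doses. It counts opportunities and does not measure bias.

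**4. What would have to happen for bias to arise.** (a) The supplied active solution is visibly tinted. (b) The contents can be seen in the syringe. (c) The checker notices and interprets the tint. (d) The checker later rates the participant, assigns causality, or tells someone who does. The documents establish none of these four steps, and the protocol text excludes none of them.

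**5. Endpoints out of reach.** Percentage change in total IgG at Week 7 (Protocol 10.3.1, SAP 9.1) is a laboratory value withheld from the site. A rater's belief about assignment does not enter it.

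**The case against.** The case for leaving the plan alone has real substance.

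- The colour descriptions overlap, and nothing shows that the supplied lots differed visibly.
- Protocol 7.1 calls the syringes blinded, and several sections defer preparation detail to the Pharmacy Manual, which may require sleeves or opaque labels. A short redaction directly after the description of RVT-1401 in 7.4 may also bear on this.
- The blinded check covers number, location and identity, not contents.
- No section makes the checker a rater, and each dosing day's score precedes that day's check.
- Number and volume of injections are matched across arms.

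All of this stands, and it limits the point. A reader might infer that the site can learn the treatment before scoring the MG scales. The documents do not support that, because it needs all four steps in the working and none is shown. A reader might also suspect the label, which Protocol 7.4 describes as a "label that includes at a minimum the study number, participant number, medication number and vial number". No section says these numbers can be decoded to a product, so no change to the label is asked for. Nor do the documents give any basis for expressing the bias in MG-ADL points.

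What the objection does not remove is that the protocol requires a blinded person at this task when an unblinded one is already available, and that it has no rule separating dosing staff from raters.

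**Conclusion.** The point holds as a potential and avoidable unblinding route for post-baseline MG-ADL, QMG, MGC and adverse-event causality. It does not hold as a finding that treatment is revealed. Exposure is at most 12 syringe checks per participant before the Week 7 scores; the size of any resulting bias is unknown. Baseline scores and the Week 7 IgG endpoint are not affected.

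The conclusion rests on the protocol text alone. If the Pharmacy Manual already requires masked contents, the visual route is closed and only the missing separation of dosing staff from raters remains. This is a cheap improvement and does not call the trial's main conclusions into question.

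**What to change.** In Protocol 7.6, for the double-blind phase only, have the dosing-time check of syringe number, location and identity done by the second unblinded staff member who already confirms preparation. The open-label check can stay as it is.

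Add one sentence: anyone who prepares, checks or gives double-blind doses does not perform MG assessments or assign adverse-event causality for that participant.

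If a blinded checker is kept, require the syringe contents to be visually masked, by cross-reference if the Pharmacy Manual already does so.

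The cost is a short wording change. No new role is created, but the second unblinded person must attend each of the six double-blind doses, and small sites will need to plan staffing so that raters stay separate. Moving the check does not alter what the participant may see; that still depends on masking.

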## **7.7. Treatment of Study Treatment Overdose**

The Sponsor does not recommend specific treatment for an overdose.

In the event of an overdose the Investigator or treating physician should:

- contact the Medical Monitor immediately,
- closely monitor the participant for AEs/SAEs and laboratory abnormalities.
- obtain a plasma sample for PK analysis within 2 days from the date of the last dose of study treatment if requested by the Medical Monitor (determined on a case-by-case basis)
- document the quantity of the excess dose as well as the duration of the overdosing in the eCRF

Decisions regarding dose interruptions or modifications will be made by the Investigator in consultation with the Medical Monitor based on the clinical evaluation of the participant.

## **7.8. Treatment After the End of the Study**

Participants will not receive any additional treatment with the study treatment from the Sponsor after completion of the study because the long-term safety and efficacy of RVT-1401 have not been established.

The Principal Investigator is responsible for ensuring that consideration has been given to the post-study care of the participant's medical condition, whether or not the Sponsor is providing specific post-study treatment.

## **7.9. Concomitant Medications and Non-Drug Therapies**

### **7.9.1. Permitted Medications and Non-Drug Therapies**

Any concomitant medication should be recorded in the study records, including the doses administered, the dates and times of administration and the reason for administration.

Refer to Section 6.2 and Section 6.3 in the study inclusion and exclusion criteria for permitted standard of care MG treatments.

### **7.9.2. Prohibited Medications and Non-Drug Therapies**

Refer to the exclusion criteria (Section 6.3) and the SRM for a list of prohibited medications.

## **8. STUDY ASSESSMENTS AND PROCEDURES**

Protocol waivers or exemptions are not allowed with the exception of immediate safety concerns. Therefore, adherence to the study design requirements, including those specified in the Time and Events Tables, are essential and required for study conduct.

This section lists the procedures and parameters of each planned study assessment. The exact timing of each assessment is listed in the Time and Events Tables, Section 8.1 and Section 8.2.

The following points must be noted:

- The Institutional Review Board (IRB)/Independent Ethics Committee (IEC) will be informed of any safety issues that require alteration of the safety monitoring scheme or amendment of the Informed Consent Form.
- The total blood volume collected will be specified within the ICF.

## 8.1. Time and Events Table (12-week follow-up without OLE)

	Screening 	Treatment Period Week 1 (Days)			Treatment Period Weekly Visit (Weeks)				Treatment Period Week 6 (Days)			Follow-up Period Weekly Visit (Weeks)							Early Withdrawal Visit	
		Day 1 (Baseline)	Day 3	Day 5	2 (Day 8)	3 (Day 15)	4 (Day 22)	5 (Day 29)	6 (Day 36)	Day 38	Day 40	7	8	9	10	12	14	16	18	
Study Timepoint (Weeks)	Within 21 Days																			
Time Window (days)			+1 day	+1 day	+/-1 day	+/-1 day	+/-1 day	+/-1 day	+/-1 day	+1 day	+1 day									
Informed consent	X																			
Inclusion/exclusion criteria	X	X																		
Demographics and medical history	X																			
Height	X																			
Body weight	X	X																		
Complete physical examination	X	X																		
Brief physical examination																			X	X
Vital signs 	X	X	X	X	X	X	X	X	X	X	X	X	X	X	X	X	X	X	X	
12-lead Electrocardiogram 	X	X			X		X		X										X	X
Pregnancy test  (females)	X	X			X	X	X	X											X	X
QuantiFERON®-TB Gold	X																			
Viral Serology	X																			
Urinalysis 	X	X			X	X	X	X	X		X								X	X
Blood chemistry and hematology 	X	X			X	X	X	X	X		X								X	X
Serum complement (CH50, C3) 		X			X	X	X	X	X		X								X	X

	Screening 	Treatment Period Week 1 (Days)			Treatment Period Weekly Visit (Weeks)				Treatment Period Week 6 (Days)			Follow-up Period Weekly Visit (Weeks)							Early Withdrawal Visit	
		Day 1 (Baseline)	Day 3	Day 5	2 (Day 8)	3 (Day 15)	4 (Day 22)	5 (Day 29)	6 (Day 36)	Day 38	Day 40	7	8	9	10	12	14	16	18	
Study Timepoint (Weeks)	Within 21 Days																			
Time Window (days)			+1 day	+1 day	+/-1 day	+/-1 day	+/-1 day	+/-1 day	+/-1 day	+1 day	+1 day	+/-2 days	+/-2 days	+/-2 days	+/-2 days	+/-2 days	+/-2 days	+/-2 days	+/- 2 days	
Immunoglobulins (IgM, IgA) 		X				X			X			X	X	X						X
RVT-1401 PK sampling 		X	X	X	X	X	X	X	X	X	X	X	X							X
Total IgG 	X	X	X	X	X	X	X	X	X	X	X	X	X	X	X	X	X	X	X	
Immunoglobins (IgG subclasses) 		X	X	X	X	X	X		X	X	X	X			X					
Anti- RVT- 1401 antibody 		X				X						X				X			X	X
Nab Assessment 		X				X						X				X			X	X
anti-AChR antibody 	X	X	X	X	X	X	X	X	X	X	X	X	X	X	X	X	X	X	X	
Drug administration		X			X	X	X	X												
Injection site reactions 		X			X	X	X	X												
MG-ADL 		X			X	X	X	X				X	X		X	X			X	
Quantitative Myasthenia Gravis (QMG) Score 	X	X			X	X	X	X				X	X		X	X			X	

	Screening 	Treatment Period Week 1 (Days)			Treatment Period Weekly Visit (Weeks)				Treatment Period Week 6 (Days)			Follow-up Period Weekly Visit (Weeks)							Early Withdrawal Visit		
		Day 1 (Baseline)	Day 3	Day 5	2 (Day 8)	3 (Day 15)	4 (Day 22)	5 (Day 29)	6 (Day 36)	Day 38	Day 40	7	8	9	10	12	14	16	18		
Study Timepoint (Weeks)	Within 21 Days																				
Time Window (days)			+1 day	+1 day	+/-1 day	+/-1 day	+/-1 day	+/-1 day	+/-1 day	+1 day	+1 day										
Myasthenia Gravis Composite (MGC) Score 		X			X	X	X	X				X	X			X	X			X	X
Myasthenia Gravis Quality of Life (MG- QOL15r) Score 		X						X				X				X	X			X	X
Satisfaction Questionnaire												X									X
Adverse events	X	X	X	X	X	X	X	X	X	X	X	X	X	X	X	X	X	X	X	X	
Concomitant medication	X	X	X	X	X	X	X	X	X	X	X	X	X	X	X	X	X	X	X	X	

1. Screening can take place over multiple days to ensure participants withhold cholinesterase inhibitors for at least 12 hours prior to the QMG and MGC assessments.
2. Vitals, ECG and blood draws for safety, PK, and PD assessment will be collected pre-dose on dosing days where specified.
3. Pregnancy tests will be collected pre-dose (via urine dipstick) on dosing days where specified. Serum pregnancy tests should be collected at screening, week 18, and early withdrawal.
4. Participants positive for anti- RVT-1401 antibody at Week 18 will be requested to return at approximately 6, 9, and 12 months post-dose for additional samples or until their result is no longer positive. However, for purposes of safety follow-up and database lock participation ends at the Week 18 visit.
5. Local injection site reactions will be assessed at approximately 10 minutes post dose.
6. MG assessments will be assessed pre-dose when collected on dosing days
7. Subjects should be instructed to withhold cholinesterase inhibitors for at least 12 hours prior to the QMG and MGC assessments.

## 8.2. Time and Events Table (With OLE and 6-week follow-up)

	Screening 	Treatment Period Week 1 (Days)			Treatment Period Weekly Visit (Weeks)				Treatment Period Week 6 (Days)			OLE and Follow-up Period Weekly Visit (Weeks)							Early Withdrawal Visit	
		Day 1 (Baseline)	Day 3	Day 5	2 (Day 8)	3 (Day 15)	4 (Day 22)	5 (Day 29)	6 (Day 36)	Day 38	Day 40	7	8	9	10	12	14	16	18	
Study Timepoint (Weeks)	Within 21 Days																			
Time Window (days)			+1 day	+1 day	+/-1 day	+/-1 day	+/-1 day	+/-1 day	+/-1 day	+1 day	+1 day	+1 day	+/-2 days	+/-2 days	+/-2 days	+/-2 days	+/-2 days	+/-2 days	+/-2 days	
Informed consent	X 	→	→	→	→	→	→	→	→	→	→	→	→	→	→	→	→	→	→	
Inclusion/exclusion criteria	X	X													X 					
Demographics and medical history	X																			
Height	X																			
Body weight	X	X																		
Complete physical examination	X	X																		
Brief physical examination																			X	
Vital signs 	X	X	X	X	X	X	X	X	X	X	X	X	X	X	X	X	X	X	X	
12-lead Electrocardiogram 	X	X			X		X		X										X	
Pregnancy test  (females)	X	X			X	X	X	X					X		X	X			X	
QuantiFERON®-TB Gold	X																			
Viral Serology	X																			
Urinalysis 	X	X			X	X	X	X				X							X	
Blood chemistry and hematology 	X	X			X	X	X	X				X							X	
Serum complement (CH50, C3) 		X			X	X	X	X				X							X	

	Screening 	Treatment Period Week 1 (Days)			Treatment Period Weekly Visit (Weeks)			Treatment Period Week 6 (Days)			OLE and Follow-up Period Weekly Visit (Weeks)								Early Withdrawal Visit		
		Day 1 (Baseline)	Day 3	Day 5	2 (Day 8)	3 (Day 15)	4 (Day 22)	5 (Day 29)	6 (Day 36)	Day 38	Day 40	7	8	9	10	12	14	16	18		
Study Timepoint (Weeks)	Within 21 Days																				
Time Window (days)			+1 day	+1 day	+/-1 day	+/-1 day	+/-1 day	+/-1 day	+/-1 day	+1 day	+1 day	+/-2 days									
Immunoglobulins (IgM, IgA) 		X				X			X			X	X	X						X	X
RVT-1401 PK sampling 		X	X	X	X	X	X	X	X	X	X	X	X	X	X	X	X	X		X	
Total IgG 	X	X	X	X	X	X	X	X	X	X	X	X	X	X	X	X	X	X	X	X	
Immunoglobins (IgG subclasses) 		X	X	X	X	X	X	X	X	X	X				X						
Anti-RVT- 1401 antibody 			X			X						X				X			X	X	
Nab Assessment 			X			X						X				X			X	X	
anti-AChR antibody 	X	X	X	X	X	X	X	X	X	X	X	X	X	X	X	X	X	X	X	X	
Drug administration			X			X	X	X	X	X			X		X	X					
Injection site reactions 			X			X	X	X	X				X		X	X					
MG-ADL 			X			X	X	X	X			X	X		X	X			X	X	
Quantitative Myasthenia Gravis (QMG) Score 	X	X			X	X	X	X				X	X		X	X			X	X	

	Screening 	Treatment Period Week 1 (Days)			Treatment Period Weekly Visit (Weeks)				Treatment Period Week 6 (Days)			OLE and Follow-up Period Weekly Visit (Weeks)							Early Withdrawal Visit	
		Day 1 (Baseline)	Day 3	Day 5	2 (Day 8)	3 (Day 15)	4 (Day 22)	5 (Day 29)	6 (Day 36)	Day 38	Day 40	7	8	9	10	12	14	16	18	
Study Timepoint (Weeks)	Within 21 Days																			
Time Window (days)			+1 day	+1 day	+/-1 day	+/-1 day	+/-1 day	+/-1 day	+/-1 day	+1 day	+1 day					+/-2 days	+/-2 days	+/-2 days	+/-2 days	+/-2 days
Myasthenia Gravis Composite (MGC) Score 		X			X	X	X	X				X	X			X	X			X
Myasthenia Gravis Quality of Life (MG- QOL15r) Score 		X						X								X	X			X
Satisfaction Questionnaire												X								X
Adverse events	X	X	X	X	X	X	X	X	X	X	X	X	X	X	X	X	X	X	X	
Concomitant medication	X	X	X	X	X	X	X	X	X	X	X	X	X	X	X	X	X	X	X	

1. Screening can take place over multiple days to ensure participants withhold cholinesterase inhibitors for at least 12 hours prior to the QMG and MGC assessments.
2. Consent for enrollment into the OLE must occur prior to Week 8.
3. Participants who complete the 6-week, randomized, double-blind treatment phase are eligible to participate in the OLE
4. Vitals, ECG and blood draws for safety, PK, and PD assessment will be collected pre-dose on dosing days where specified.
5. Pregnancy tests will be collected pre-dose (via urine dipstick) on dosing days where specified. Serum pregnancy tests should be collected at screening, week 18, and early withdrawal.
6. Participants positive for anti- RVT-1401 antibody at Week 18 will be requested to return at approximately 6, 9, and 12 months post-dose for additional samples or until their result is no longer positive. However, for purposes of safety follow-up and database lock participation ends at the Week 18 visit.
7. Local injection site reactions will be assessed at approximately 10 minutes post dose.
8. MG assessments will be assessed pre-dose when collected on dosing days.
9. Subjects should be instructed to withhold cholinesterase inhibitors for at least 12 hours prior to the QMG and MGC assessments.

### **8.3. Screening and Critical Baseline Assessments**

Screening assessments are outlined in the Time and Events Table, (Section 8.1). The following demographic parameters will be captured: year and month of birth, sex, race and ethnicity.

Medical/medication history will be assessed as related to the inclusion/exclusion criteria listed in Section 6.

Written informed consent must be obtained prior to performance of any study related procedures. Screening can take place over multiple days. In particular, the protocol requirement to withhold cholinesterase inhibitors for at least 12 hours prior to the QMG and MGC assessments may require participants to return on a separate day during the screening period to ensure they sign an informed consent form prior to withholding this treatment.

